20.1 Ethical Conduct of the Study

This study shall be conducted in accordance with ethical principles that have their origin in the Declaration of Helsinki, the Law on Securing Quality, Efficacy and Safety of Products Including Pharmaceuticals and Medical Devices, GCP, and the protocol.

20.2 Institutional Review Board

The IRB shall review the study from ethical, scientific, medical, and pharmaceutical perspectives to determine the implementation and continuation of the study based on the investigator's brochure, protocol, informed consent form, and written information.

20.3 Protection of Subject Confidentiality

When enrolling subjects and filling in the CRFs, the investigator will specify each subject using a subject ID code. In addition, subject confidentiality shall be protected at the time of direct access to the source data, publication to medical journals, and data submission to the regulatory authorities.

21. Retention of Records

(1) Records to be retained at the study site

The record storage manager assigned by the head of the study site will store records related to the study at the study site until date 1) or 2) below, whichever comes later. However, when the sponsor deems it necessary to retain these records for a longer period, the storage period and method of storage shall be decided upon discussion with the sponsor.

If the sponsor decides not to attach the clinical study results collected from the study to the application for marketing approval, the sponsor will report this decision and the reason to the head of the study site in writing.

In addition, when the marketing approval of the investigational product is obtained, or when the marketing approval is not obtained and development is terminated, the sponsor will report these matters to the head of the study site in writing.

- 1) The date of marketing approval of the investigational product (date of approval for partial changes for approval for additional indications) (When development is terminated, or when a notification has been received indicating that the study results will not be attached to the application, this will be 25 years from the date of receiving the notification.)
- 2) Twenty-five years from the date of study termination or completion

(2) Records to be retained by the sponsor

The sponsor will store records relating to the study at the sponsor until date 1) or 2) below, whichever comes later.

Confidential

- 1) Twenty-five years from the date of marketing approval of the investigational product (date of approval for partial changes for approval for additional indications) or date of completion of reexamination (When development is terminated, this will be 25 years from the date of the decision for development termination.)
- 2) Twenty-five years from the date of study termination or completion

22. Payment to the Subjects

Payment to the subjects and the study site will be made according to the contract or agreement between the study site and the sponsor.

23. Compensation for Health Hazards and Insurance

23.1 Compensation for Health Hazards

If any health hazards to the subjects are caused by this study, the sponsor assures appropriate compensation for such health hazards, according to the standards specified by the sponsor, except in cases where it is determined that the health hazard is not related to the study. (This compensation includes medical expenses, medical allowances, and compensation money.) In such cases, the sponsor will not impose a burden on the subjects regarding proof of the relationship to the study treatment.

## ABBREVIATIONS

Abbreviations	Definitions
AE	adverse event
ALT	alanine transaminase
ALP	alkaline phosphatase
AST	aspartate transaminase
BLQ	below limit of quantification
BMI	body mass index
CI	confidence interval
CV	coefficient of variation
DP	decimal places
ECG	electrocardiogram
MedDRA	medical dictionary for regulatory activities
MTPC	Mitsubishi Tanabe Pharma Corporation
PK	pharmacokinetics
PT	preferred term
SAP	statistical analysis plan
SAE	serious adverse event
SAF	safety population
SD	standard deviation
SOC	system organ class
TEAE	treatment emergent adverse event
TESAE	treatment emergent serious adverse events
WHO	World Health Organization

## LIST OF PK PARAMETERS

Parameters	Definitions
AUC 0-24	Area under the plasma concentration-time curve from zero up to 24 hour
AUC 0-t	Area under the plasma concentration-time curve from zero up to the last quantifiable concentration time point
AUC 0-∞	Area under the plasma concentration-time curve from zero up to infinity with extrapolation of the terminal phase
AUC% 0ex	Area under the (plasma) concentration-time curve extrapolated from the last quantifiable concentration time point to infinity in % of the total AUC 0-∞
Ae 0-24	Cumulative urinary excretion amount of drug from zero to 24 hour
C max	Maximum plasma concentration after administration
C last	Last quantifiable concentration
CL/F	Apparent total clearance
CL r	Renal clearance
K el	Elimination rate constant from the central compartment
LLOQ	Lower limit of quantification
LOQ	Limit of quantification
MRT	Mean residence time
NC	Not calculated
t 1/2	Terminal elimination half-life in plasma concentration-time course
V ss /F	Apparent volume of distribution at steady state
V z /F	Apparent volume of distribution during terminal phase
Ae%	Urinary excretion ratio of drug

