In terms of PK, after a single dose of edaravone solution or suspension in the fasting state, plasma concentrations reached C_{max} 0.3 to 0.4 hours and 0.4 to 0.8 hours after dose, respectively. Subsequently they were excreted in 2 and 3 phases, and $t_{1/2}$ of the terminal phase were 2.4 to 3.2 hours and 5.1 to 11.8 hours, respectively. C_{max} and AUC of edaravone increased more than dose proportional manner over a dose range of 30 to 300 mg. Plasma concentrations of sulfate conjugate and glucuronide conjugate, both are edaravone metabolites, reached C_{max} 0.5 to 1.4 hours and 0.5 to 1.1 hours after dose, respectively. They were excreted from plasma, with $t_{1/2}$ of 4.9 to 7.9 hours and 2.8 to 5.9 hours, respectively. Meal-effect examination after administration of 200 mg suspension (200 mg/10 mL 0.1% polyvinyl alcohol solution) showed that when edaravone was administered 30 minutes after a meal, C_{max} and AUC of plasma edaravone decreased to 18.2% and 39.1% of those when it was administered in the fasting state, respectively. Comparison between plasma concentrations in Caucasian subjects and those in Japanese subjects after administration of 200 mg suspension (200 mg/10 mL) showed that C_{max} and AUC of plasma edaravone in

Confidential

Caucasian subjects were 75% and 79% of those in Japanese subjects, respectively. Five-day multiple doses resulted in no accumulation in plasma concentrations of edaravone.

A clinical pharmacology study of oral edaravone in healthy adult male subjects (as a drug interaction study and as a preliminary study on dosage and administration) (MT-1186-J02 study) is ongoing, and edaravone oral suspension was orally administered to 84 subjects. Drug interaction, safety, and tolerability of 120 mg edaravone oral suspension are being investigated in 66 subjects; and PK, effects of race or meal, safety, and tolerability of 100 mg are being investigated in 18 subjects.

In terms of safety, no serious adverse events occurred. A total of 27 adverse events were observed in 84 subjects. Among them, 7 adverse events (diarrhoea 4, ALT increased 2, and AST increased 1) were assessed as causally related to the administration. All of them were mild in severity and rapidly resolved. No adverse events led to discontinuation in any subject.

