9.2.4 Pharmacokinetic assessments

Blood sampling will be performed for measurement of plasma concentrations of unchanged edaravone, sulfate conjugate, and glucuronide conjugate, and urine sampling will be performed for measurement of urine concentrations of them. The investigator (or subinvestigator) or study collaborator will record the dates and times of the blood and urine sampling and the sampled urine volume in the CRF. The measurement will be conducted in the drug concentration measurement site.

If any other assessments are scheduled at the same time point of blood sampling for plasma drug concentration measurement, blood sampling will be performed at the exact scheduled time point, and other assessments will be performed before or after the blood sampling. In principle, a 12-lead ECG and vital signs (except for body temperature) will be measured before the blood sampling for plasma drug concentration measurement and safety assessment. Urine will be forced to void 24 hours after administration. Urine will not be collected from subjects if collection is difficult.

The acceptable time range for the time of each blood or urine sampling (forced void) will be

Confidential

specified in a separate document.

9.2.4.1 Measurement of plasma concentrations of unchanged edaravone, sulfate conjugate, and glucuronide conjugate

Time points and volume of blood sampling

(a) Time points of blood sampling

Day 1	Before investigational product administration, 0.083, 0.25, 0.5, 0.75, 1, 1.5, 2, 4, 6, 8, 10, and 12 hours after administration
Day 2	24 hours after investigational product administration

(b) Frequency of blood sampling: 14

(c) Volume of blood sampling: 5.5 mL, Total: 77 mL (per subject)

9.2.4.2 Measurement of urine concentrations of unchanged edaravone, sulfate conjugate, and glucuronide conjugate

Urine volume will be measured at voiding and the urine specimen will be processed (see Section 9.2.4.3). Urine will be forced to void before administration and 24 hours after administration. Urine will not be collected from subjects if collection is difficult.

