#### Urine PK sampling

Nominal Time Point	Window
Predose	Within 60 min before dosing
Voluntary Urine	–
Forced micturition at 24 h after dosing	Nominal time point $\pm$ 30 min

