### Appendix 1 Pharmacokinetic Parameter Calculations

- Actual blood sampling times will be used in the calculation of pharmacokinetic parameters
- All concentrations below the LLOQ will be set at zero for pharmacokinetic calculations
- When  $K_{el}$  is missing (or cannot be determined),  $t_{1/2}$ ,  $AUC_{0-\infty}$ ,  $AUC\%_{ex}$ ,  $CL/F$ ,  $MRT$ ,  $V_z/F$  and  $V_{ss}/F$  will not be calculated.

PK Parameter Calculations		
Parameters	Unit	Calculation
$C_{max}$	ng/mL	will be determined by visual inspection
$AUC_{0-\infty}$	ng·h/mL	$AUC_{0-\infty} = AUC_{0-t} + C_{last} / K_{el}$ $C_{last}$ : last measurable concentration
$AUC\%_{ex}$	%	$AUC\%_{ex} = (AUC_{0-\infty} - AUC_{0-t}) / AUC_{0-\infty} \times 100$
$AUC_{0-t}$	ng·h/mL	will be calculated using the linear trapezoidal method and actual times $AUC_{0-t} = \sum_{i=1}^n \frac{t_i - t_{i-1}}{2} (C_{i-1} + C_i)$
$AUC_{0-24}$	h·ng/mL	will be calculated using time until 24 h drug concentration
$t_{max}$	h	Measured time of $C_{max}$
$t_{1/2}$	h	$t_{1/2}$ will be determined as: $t_{1/2} = \log_e(2) / K_{el}$
$K_{el}$	/h	The exponential rate constant of the terminal phase, $k_{el}$ , will be estimated by log-linear regression, if determinable. The number of data points included in the regression will be determined by visual inspection. Wherever possible, a minimum of 3 data points will be used in the estimation of $k_{el}$ .  During the analysis, this calculation method repeats regressions using the last three points with non-zero concentrations, then the last four points, last five, etc. The time of maximum concentration ( $t_{max}$ ) will be excluded from the estimation of $K_{el}$ . Points with a value of zero for the dependent variable are excluded. For each regression, an adjusted $R^2$ is computed $Adjusted R^2 = 1 - \frac{(1 - R^2) \times (n - 1)}{(n - 2)}$ where n is the number of data points in the regression and $R^2$ is the square of the correlation coefficient.

		
The regression with the largest adjusted R^2 is selected to estimate Kel, with these caveats:
 
 
- If the adjusted R^2 does not improve, but is within 0.0001 of the largest adjusted R^2 value, the regression with the larger number of points is used.
 
- kel must be positive, and calculated from at least three data points.
 

CL/F	L/h	$CL/F = \frac{\text{Dose}}{AUC_{0-\infty}}$

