MRT	h	$AUMC_{0-\infty} = \sum_{i=1}^n \frac{(t_i - t_{i-1})(t_i \times C_i + t_{i-1} \times C_{i-1})}{2} + \frac{t \times C_t}{K_{el}} + \frac{C_t}{(K_{el})^2}$ $MRT_{0-\infty} = \frac{AUMC_{0-\infty}}{AUC_{0-\infty}}$
V z /F	L	$V_z/F = CL/F \times \frac{1}{K_{el}}$
V ss /F	L	$V_{ss}/F = MRT \times CL/F$
Number of Kel points	-	will be determined using number of points used in computing Kel. If Kel cannot be estimated, zero.
Lower Limit of Kel	h	will be determined using lower limit on time to be included in the calculation of Kel
Upper Limit of Kel	h	will be determined using upper limit on time to be included in the calculation of Kel
Ae	mg	urine concentration × urine volume
Ae%	%	Ae / Dose
CLr	L/h	$CLr = \frac{Ae}{AUC_{0-\infty}}$

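### Renal clearance divides a 0–24 h urinary amount by AUC0-∞, so CLr of unchanged edaravone is biased low, more so at longer half-lives

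*SAP*

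**What the plan says.** **Numerator.** The SAP's List of PK Parameters defines Ae0-24 as "Cumulative urinary excretion amount of drug from zero to 24 hour". Protocol 9.2.4.2 sets the collection: "Urine will be forced to void before administration and 24 hours after administration". The last urine entry in SAP 7.2 is "Forced micturition at 24 h after dosing", with a window of ±30 min, and no later collection is planned. The Ae row of SAP Appendix 1 reads only "urine concentration × urine volume" and names no interval. The parameter list and the collection schedule leave 0–24 h as the only possible reading.

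**Denominator.** The CLr row of Appendix 1 divides Ae by AUC0-∞. The parameter list defines AUC0-∞ as "Area under the plasma concentration-time curve from zero up to infinity with extrapolation of the terminal phase", and Appendix 1 obtains it by adding Clast/Kel to AUC0-t.

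**The matching AUC is already planned.** AUC0-24 is a listed parameter in SAP 2.3, and Appendix 1 says it "will be calculated using time until 24 h drug concentration". It is not used for CLr.

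**Missing Kel.** Appendix 1 lists the parameters that will not be calculated when Kel cannot be determined: t1/2, AUC0-∞, AUC%ex, CL/F, MRT, Vz/F and Vss/F. CLr is not on that list.

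Neither document gives a reason for pairing a 24 h amount with an AUC to infinity.

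**The concern.** Renal clearance is the amount excreted over an interval divided by the plasma AUC over the same interval. Here the numerator stops at 24 h and the denominator does not, so the ratio understates CLr by the fraction of exposure that falls after 24 h. That fraction depends on each patient's terminal half-life and on how much of the AUC lies in the terminal phase. The error therefore differs between patients, and it does not average out over nine of them.

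There is also a structural cost. CLr needs no extrapolation, but this formula makes it inherit the error in Kel and Clast. A patient without a determinable Kel has no AUC0-∞ and so no CLr, even when Ae0-24 and AUC0-24 are both available. In a study of nine, one such loss is 1/9, or 11%, of the CLr values.

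CLr of unchanged edaravone is a listed parameter in a study whose only objective is pharmacokinetic.

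**Working it through.** The documents give no CLr value or bias to reproduce, so the check derives the error from the SAP's formula.

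**Inputs from the documents**
- Urine interval: 0–24 h (SAP List of PK Parameters; Protocol 9.2.4.2; SAP 7.2).
- CLr = Ae/AUC0-∞ and AUC0-∞ = AUC0-t + Clast/Kel (SAP Appendix 1).
- Terminal half-lives in the earlier phase I study in healthy men, for solution and suspension in that order: "of the terminal phase were 2.4 to 3.2 hours and 5.1 to 11.8 hours, respectively" (Protocol Section 1(3), clinical study results). The suspension range is therefore 5.1 to 11.8 h. The same text describes a three-phase decline for the suspension.

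**Assumed, because the documents do not give it**
- Terminal phase's share of AUC0-∞, called f: 10% to 30%. A share of 100% (mono-exponential decline) is shown as a mathematical ceiling only.

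**Step 1: what the formula estimates.** With constant renal clearance, Ae0-24 = CLr × AUC0-24. The planned estimate is then

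Ae0-24/AUC0-∞ = CLr × AUC0-24/AUC0-∞.

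Its relative bias is −AUC24-∞/AUC0-∞.

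**Step 2: size of the tail.** Once absorption and the faster phases are over, AUC24-∞/AUC0-∞ ≈ f × 2^(−24/t1/2), so

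bias ≈ −f × 2^(−24/t1/2).

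**Step 3: numbers.**
- 2^(−24/5.1) = 0.0383
- 2^(−24/11.8) = 0.2442

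| t1/2 | f = 10% | f = 20% | f = 30% | ceiling, f = 100% |
|---|---|---|---|---|
| 5.1 h | −0.4% | −0.8% | −1.1% | −3.8% |
| 11.8 h | −2.4% | −4.9% | −7.3% | −24.4% |

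**Step 4: how realistic the ceiling is.** The protocol gives Cmax 1,195 ng/mL and AUC0-∞ 1,738 ng·h/mL after 60 mg IV. Borrowed as a rough scale, AUC/Cmax = 1,738/1,195 ≈ 1.5 h. A mono-exponential curve with t1/2 11.8 h would have AUC/Cmax = 11.8/ln 2 ≈ 17 h. The ceiling is therefore not a plausible expectation. On the same borrowed AUC, with t1/2 11.8 h (Kel = 0.0587/h), a 5% bias needs a 24 h concentration of 0.05 × 1,738 × 0.0587 ≈ 5.1 ng/mL, and a 1% bias needs about 1.0 ng/mL.

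**Step 5: check under the SAP's own calculation rules.** An illustrative three-phase profile was run through the SAP's sampling times, linear trapezoid and adjusted-R² rule for Kel. It assumed an AUC0-∞ of 1,738 ng·h/mL, an absorption rate of 6/h, earlier half-lives of 0.5 and 2 h sharing the non-terminal area 75:25, and f from 5% to 30%. Replacing AUC0-∞ with AUC0-24 raised CLr by 0.1% to 1.1% at 5.1 h and by 0.6% to 6.5% at 11.8 h, in line with Step 3.

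**Step 6: a reading per patient.** If the 24 h sample is the last quantifiable one, AUC0-t equals AUC0-24. The planned CLr is then the matched CLr × (1 − AUC%ex/100), so the estimated shortfall is that patient's own AUC%ex. The SAP lists AUC%ex but does not summarise it.

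**The case against.** The case for leaving the formula alone concedes the mismatch and argues that little follows from it.

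- **Size.** At 5.1 h the bias is about 1% or less. The −7.3% figure needs both the longest reported half-life and a 30% terminal share. Neither the share nor the 24 h concentration is in the documents, and the half-lives come from healthy men at 30 to 300 mg, not from ALS patients at 105 mg. This stands: the size is uncertain and probably a low single-digit percentage.
- **Direction.** The SAP sets values below quantification to zero. If 12 h is the last measurable sample and 24 h is set to zero, the linear trapezoid gives a 12–24 h area of 6 × C12, against C12/Kel in AUC0-∞. The computed AUC0-24 then exceeds AUC0-∞ when the estimated t1/2 is below 6 × ln 2 ≈ 4.2 h. This stands as an edge case, but it lies outside the reported 5.1 to 11.8 h and comes from the zero imputation, not from the interval mismatch.
- **Other errors remain.** In the illustrative profile the linear trapezoid overstated AUC and lowered CLr by about 3% to 4% with either denominator. SAP 7.3 also sets missing data to zero for Ae. This stands: matching the intervals does not make CLr free of error. It is no reason to keep an avoidable error.
- **Missing Kel.** Leaving CLr off the list is arguably editorial, since CLr cannot be computed without AUC0-∞. That is true, but the dependence itself is unnecessary.
- **Importance.** CLr is one of 14 parameters for unchanged drug, summarised descriptively with no test or decision rule. This stands, and it limits the consequence.

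**Conclusion.** The concern holds. The SAP pairs a 0–24 h urinary amount with an AUC to infinity, so CLr is understated by the fraction of exposure after 24 h. For a given terminal share, the understatement grows with half-life. It is −0.4% to −1.1% at t1/2 5.1 h and −2.4% to −7.3% at 11.8 h.

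These figures rest on constant renal clearance, a terminal share of 10% to 30% (assumed) and half-lives carried over from healthy men. The mono-exponential values of −3.8% and −24.4% are limits, not expectations. The downward direction holds for the true areas; the zero-imputation edge case does not change that within the reported half-life range.

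The correction is worth making because the definition is wrong and ties CLr to Kel without need. The likely numerical effect is modest.

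**What to change.** In SAP Appendix 1, change the CLr row to CLr = Ae0-24/AUC0-24 and label the Ae row as Ae0-24. This removes the interval mismatch and the dependence on Kel, so the omission of CLr from the missing-Kel list no longer matters. Because CLr would then rest on AUC0-24, add one sentence saying how AUC0-24 is handled when the 24 h sample is missing or below quantification; the AUC0-24 row does not say.

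The cost is one formula, one label and one sentence. No new samples or parameters are needed. Protocol 13.5 provides the route. A change to the protocol's planned analysis before data lock is recorded with its reason in the SAP and study report. A change of method after lock goes into a revised SAP and the report, with results before and after the change shown separately.

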Attachment 1 Administrative Structure

Attachment 2 El Escorial Revised Airlie House Criteria

Attachment 3 ALSFRS-R

Confidential

List of Abbreviations

Abbreviations	Unabbreviated expressions
ALS	Amyotrophic lateral sclerosis
BCRP	Breast cancer resistance protein
BMI	Body mass index
CYP	Cytochrome P450
EDC	Electronic data capture
FSH	Follicle stimulating hormone
GCP	Good clinical practice
HBs	Hepatitis B surface
hCG	Human chorionic gonadotrophin
HCV	Hepatitis C virus
HIV	Human immunodeficiency virus
HR	Heart rate
IC ₅₀	drug concentration associated with 50% inhibition
ICH	International Council for Harmonization of Technical Requirements for Pharmaceuticals for Human Use
MedDRA	Medical Dictionary for Regulatory Activities
OAT	Organic anion transporter
PK	Pharmacokinetic(s)
QTcF	Fridericia's correction of QT interval
SAE	Serious adverse event
SOD	Superoxide dismutase
TEAE	Treatment-emergent adverse event
UGT	UDP-glucuronosyl transferase

Confidential

List of Abbreviations for Pharmacokinetic (PK) Parameters

Abbreviations	Unabbreviated expressions
Ae	Cumulative amount of drug excreted in urine
Ae%	Cumulative percentage of drug excreted in urine
AUC	Area under the plasma concentration-time curve
CL/F	Apparent total clearance
CL _r /F	Apparent renal clearance
C _{max}	Maximum plasma concentration
K _{el}	Apparent terminal elimination rate constant
MRT	Mean residence time
t _{1/2}	Terminal elimination half-life
t _{max}	Time to reach maximum plasma concentration
V _{ss} /F	Apparent distribution volume at steady state
V _z /F	Apparent distribution volume at elimination phase

Definition of Term

Term	Definition
Study period	Period from the time of obtaining the informed consent to the time of completion of the end-of-study assessment or discontinuation assessment (for subjects who have entered into the follow-up period, to the time of completion or termination of the follow-up)

Confidential

Protocol Summary

1 Study Title

Clinical Pharmacology Study of Oral Edaravone in Patients with Amyotrophic Lateral Sclerosis (ALS)

2 Study Objectives

To evaluate the pharmacokinetics (PK) of single doses of edaravone oral suspension in Patients with Amyotrophic Lateral Sclerosis (ALS)

3 Subjects

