5.2 Dose and Dosing Regimen

After fasting for at least 10 hours, Patients will receive the edaravone oral suspension 105 mg (105 mg/5 mL) orally.

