**8.4.2. Pharmacokinetic Parameters for unchanged edaravone, sulfate conjugate, and glucuronide conjugate**

The PK parameters listed in Section 2.3 will be calculated for each subject using non-compartmental model. The PK parameters will be listed and summarized. The PK parameters listed as other PK parameters will not be summarized. The urinary pharmacokinetic parameters will be listed and summarized. The urinary pharmacokinetic parameters at pre-dose will not be summarized.

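### The SAP's Vss/F rule gives steady-state volume plus mean absorption time × CL/F after an oral dose, but it is reported as a steady-state volume

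*SAP*

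**What the plan says.** Both documents give Vss/F a steady-state meaning. The SAP's List of PK Parameters calls it "Apparent volume of distribution at steady state", and the protocol's list of PK abbreviations calls it "Apparent distribution volume at steady state". MRT is expanded only as mean residence time, with no split between absorption and disposition.

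The protocol (section 10.1) leaves the calculation methods to the SAP. SAP Appendix 1 defines MRT as AUMC from zero to infinity divided by AUC from zero to infinity, CL/F as dose over that AUC, and Vss/F as MRT times CL/F.

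The route is oral: in the Protocol Summary, section 5.2, "Patients will receive the edaravone oral suspension 105 mg (105 mg/5 mL) orally". There is no intravenous arm. Neither document mentions a mean absorption time, an absorption correction, or the fact that this MRT comes from an oral profile.

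Vss/F is one of the 14 parameters listed for unchanged edaravone (protocol section 5.4.2, SAP section 2.3). SAP section 8.4.2 states: "The PK parameters will be listed and summarized".

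**The concern.** MRT × clearance gives a steady-state volume when MRT is the disposition MRT, that is, the mean time a molecule spends in the body after reaching the circulation. After an oral dose, AUMC/AUC also counts the time spent being absorbed. The tables would therefore carry a steady-state label on a quantity that depends partly on how fast the suspension is absorbed.

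Two patients with the same Vss/F and CL/F but different absorption speed have different target values, and the label would present the gap as a difference in distribution. The study's only objective is to describe PK in patients with ALS, so a reader could take such a difference for a disease effect, or set the number beside an intravenous Vss. The documents plan neither use, but the label does not warn against either.

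**Working it through.** The plan states no value for MRT, MAT or Vss/F, so there is no figure to reproduce. The check is whether the rule matches the label, and how large the difference could be.

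**Identity.** With linear kinetics, mean times add:
- MRT(oral) = MRT(disposition) + MAT, and MRT(disposition) = Vss/CL.
- MRT(oral) × CL/F = (Vss/CL) × (CL/F) + MAT × CL/F = Vss/F + MAT × CL/F.

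Dividing by F rescales for bioavailability; it does not remove an additive term. The identity is approximate here, because protocol section 1 (3) 2) says Cmax and AUC "of edaravone increased more than dose proportional manner over a dose range of 30 to 300 mg".

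**Inputs for size.**
- Dose: 105 mg oral.
- AUC: 1,738 ng·h/mL after 60 mg intravenously over 60 minutes (protocol section 1 (3) 2)). Using it for the oral dose is an assumption. Protocol section 8.3 cites a study to verify bioequivalence of 105 mg oral with 60 mg intravenous, but gives no result.
- MAT: not given. Peak times for solution and suspension are "0.3 to 0.4 hours and 0.4 to 0.8 hours after dose, respectively", so absorption of the suspension is fast but not instantaneous. Assumed range: 0.33 to 1.0 h.

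**Absorption term.** CL/F = 105 mg / 1.738 mg·h/L = 60.4 L/h, so each 0.1 h of MAT adds 6.0 L:
- MAT 1/3 h: 20.1 L
- MAT 0.5 h: 30.2 L
- MAT 0.75 h: 45.3 L
- MAT 1.0 h: 60.4 L

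If oral AUC were 125% or 80% of the intravenous value, CL/F would be 48.3 or 75.5 L/h, and the range over the same MAT values would be 16.1 to 75.5 L.

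**Numerical check of the identity.** Take an assumed linear three-compartment model with first-order absorption, true Vss/F 105.0 L and disposition MRT 1.74 h. Exact integration of the SAP formulas gives 135.2 L at MAT 0.5 h (105.0 + 30.2) and 165.4 L at MAT 1.0 h (105.0 + 60.4). In this example the excess at MAT 0.5 h is 30.2/105.0 = 29%.

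**Why the net error is not fixed.** The reported value also carries sampling and terminal-slope error. Appendix 1 says of the Kel fit that "this calculation method repeats regressions using the last three points with non-zero concentrations, then the last four points, last five, etc", and sets values below the quantification limit to zero. At the 14 planned sampling times, without such values, the same model gives 122.6 and 147.8 L: above the true 105.0 L, but below the exact targets.

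A limiting case shows that the sign can change. Let the slow phase carry a fraction f of AUC with mean time τ = half-life / 0.693, and suppose it is missed entirely. Then:
- Reported MRT = [MRT(disposition) + MAT − f × (τ + MAT)] / (1 − f), and CL/F becomes 60.4 / (1 − f).
- Assume f = 10%, half-life 11.8 h (τ = 17.0 h), disposition MRT 2.8 h, MAT 1/3 h. MRT = (3.133 − 1.736)/0.9 = 1.55 h and CL/F = 67.1 L/h, so the reported volume is about 104 L against a true 2.8 × 60.4 = 169 L.
- Assume f = 2%, half-life 5.1 h (τ = 7.36 h), disposition MRT 1.0 h, MAT 1/3 h. MRT = (1.333 − 0.154)/0.98 = 1.20 h and CL/F = 61.6 L/h, so the reported volume is about 74 L against a true 60.4 L.

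These are bounding illustrations, not estimates for this study.

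**The case against.** The strongest reply is that this is a labelling matter. MRT × CL/F is printed in full beside an oral dose, the volume is called apparent, and nothing is hidden. That stands as far as it goes: the formulas are open. But the label gives the number a meaning, steady-state volume, that the formula does not deliver, and the output tables may show the label without the derivation.

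A second reply is that nothing depends on Vss/F. This also stands. The analysis is descriptive, the sample of 9 rests on no calculation, and no test, comparison or decision uses this parameter.

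A third reply is that the size cannot be pinned down, and this is right. Peak time does not determine MAT. The protocol reports terminal half-lives of 2.4 to 3.2 h for the solution but 5.1 to 11.8 h for the suspension, so the suspension's slow phase may partly reflect slow absorption. Any percentage error, or any share of modelled cases with a given error, would depend on how the assumed cases were chosen.

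A reader might infer that the reported Vss/F will always be too high by MAT × CL/F. The documents do not support that: they give neither the quantification limit nor the disposition profile, and the limiting cases above go both ways.

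**Conclusion.** The concern holds as a mismatch between label and rule. After a single oral dose, Appendix 1 targets Vss/F + MAT × CL/F, while both documents name the result a steady-state volume and neither states the absorption term. The algebra is firm under approximately linear kinetics.

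The absorption term of 20 to 60 L rests on two assumptions that the documents do not confirm: equal oral and intravenous AUC, and a MAT of 0.33 to 1.0 h. The net error of the reported value has no fixed size or sign.

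The consequence is small. A reader might infer that the wider PK results are compromised. They are not: the formulas for AUC, Cmax and CL/F do not use MRT. This is a point to consider, limited to how MRT and Vss/F are named and read.

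**What to change.** In the SAP's List of PK Parameters, in Appendix 1 and in the output tables:
- label MRT as *oral MRT, includes mean absorption time*;
- label the volume as *MRT(oral) × CL/F, includes MAT × CL/F*, so that it is not reported as a steady-state volume.

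Alternatively, drop Vss/F and record this in SAP section 10 as a change from the protocol, which lists it in sections 5.4.2 and 10.1. If the data are already locked, use the route in protocol section 13.5: a revised SAP and the Clinical Study Report. With no intravenous arm, MAT cannot be estimated within the study, so an in-study correction is not available.

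Relabelling is a wording change that needs no new data and no re-analysis. It does not remove terminal-slope or quantification-limit error, which is a separate matter. Dropping Vss/F costs one protocol-listed descriptive parameter.
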